 - Person unable to express consent and who is not subject to a legal protection measure

Study Procedures/Frequency:

Subjects will be followed by the Investigator according to clinical practice, with formal (per protocol) assessments conducted at the Screening/Baseline and at other protocol Clinic Visits. Study visits will occur at Screening/Baseline, Weeks 1, 4, 8, 12, 16 and 24. After the Week 24 visit subjects will return to the clinic every 12 weeks for study assessments. There will be a 4-week follow up by telephone after the subject's End of Treatment (EOT) Visit.

If a subject withdraws consent, they should return for an ED Visit within 14 days following the last dose and they should have a Safety Follow-Up (FU) Visit 4 weeks after the ED Visit. Subjects will then be contacted for Vital Status every 24 weeks after the Safety Follow Up Visit by telephone until study completion.

Assessments that will be done at each visit can be found in the Schedule of Assessments ([Table 1](#)).

Test Product, Dose, and Mode of Administration:

Capsules of AV-101 inserted into a dry powder inhaler device for administration to subjects' lungs by inhalation.

Subjects entering the LTE study from the Phase 2b and Intermediate Parts of AV-101-002:
Capsule strength: 5 mg, 17.5 mg, or 35 mg AV-101. Administered Doses (2 capsules): 10 mg, 35 mg, or 70 mg AV-101, BID.

Subjects entering the LTE study from the Phase 3 Part of AV-101-002: AV-101 optimal dose, BID

If a subject down titrated the dose of AV-101 in Study AV-101-002 and successfully completed 24 weeks of treatment, the subject should begin the LTE study with 2 capsules BID. If the subject did not tolerate the 2 capsules, they may down titrate to one capsule in the LTE. At the time of the optimal dose selection and transition to the optimal dose in subjects who have down titrated in the LTE, the Investigator should decide whether it is clinically appropriate to transition these subjects given the tolerability history and optimal dose selection (Investigators will be unblinded to the treatment dose at this time). Down titration after subjects have switched to the optimal dose will be permitted.

Statistical Methods:

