1. Screening assessments may be performed at the AV-101-002 Week 24 Visit. Study treatment re-randomization shall occur after all AV-101-002 Week 24 procedures are completed for subjects previously randomized to placebo, if LTE participation starts prior to identifying the optimal dose. All LTE participants will be treated with the optimal dose once that dose is identified, unless participants have been down titrated.
2. Subjects discontinuing study treatment must return to the site within 14 days for safety assessments; if this assessment does not correspond with a scheduled study visit, then an Early Discontinuation (ED) Visit will be performed. If the subject is unwilling or unable to come into the clinic for the ED or the End of Treatment Visit, then this visit with as many assessments as possible can be conducted by telephone.
3. The Safety Follow-Up Visit will be performed 30 days (± 2 days) after the ED Visit.
4. A focused physical examination (PE) will be performed at Baseline and clinic post-baseline visits.
5. Height will be recorded at the Screening Visit using the measurement taken from AV-101-002.
6. Urine pregnancy test for females of childbearing potential only. Additionally, home urine pregnancy testing is required every 4 weeks between study visits. When home pregnancy testing is required, a telephone call to the subject is required to confirm the test date, result of the test, lot number, and expiration date of the test (see Section 7.8). NOTE: Follicle Stimulating Hormone (FSH) test may be performed at Screening, per Investigator's discretion to confirm post-menopausal state. A reminder to perform home pregnancy testing is given during phone visits at Weeks 8, 16 and 20.
7. Resting Transthoracic Echocardiography, PFT's and DLCO to be performed every 24 weeks following Week 24 Visit.
8. Randomization or study drug allocation will be performed by IWRS.
9. Testing includes FEV₁, FVC, and peripheral oxygen saturations.
10. Vital Status will be collected every 24 weeks after the Safety Follow Up Visit by telephone until study completion.

1 Introduction

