3.1 Overall Design

Figure 1: Study Design of Study AV-101-003

For Subjects Entering the LTE from the Phase 2b and Intermediate Parts of AV-101-002

For Subjects Entering the LTE from the Phase 3 Part of AV-101-002

- A. Screening/Baseline Visit and procedures for the LTE will be conducted at the Week 24 Visit for AV-101-002.
- B. Once the optimal dose is selected for the parent Phase 3 Part of AV-101-002, subjects who enter the LTE from the Phase 2b Part and the Intermediate Part of AV-101-002 will be transitioned to the optimal dose.
- C. Once the AV-101 optimal dose has been selected, the LTE will no longer be blinded. Subjects enrolled during the Intermediate Part of AV-101-002 that enter the LTE study after the optimal dose is selected will be assigned to that dose upon completion of the Week 24 Visit for AV-101-002.

The doses administered in the Phase 2b and Intermediate parts of Study AV-101-002 are 10 mg, 35 mg, and 70 mg BID. In the LTE study subjects will continue on these doses and placebo subjects will be re-randomized to one of these active doses until such time as the optimal dose has been selected from the Phase 2b data based upon efficacy, safety, and tolerability. Once the optimal dose has been selected subjects in the LTE will be transitioned to the optimal dose. Subjects enrolled during the Intermediate Part of AV-101-002 that enter the LTE study after the optimal dose is selected will be assigned to that dose upon completion of the Week 24 Visit for AV-101-002. Subjects on the optimal dose or placebo in the Phase 3 Part of AV-101-002 will continue in the LTE at the optimal dose.

The schedule of activities and visit frequency will be similar to the parent study (AV-101-002) for the first 24 weeks of the LTE ([Table 1](#)). Thereafter, the interval between study visits will be increased to every 3 months. In the LTE study the quality-of-life instrument used will be the emPHasis-10 questionnaire. Investigators are encouraged to collect RHC hemodynamics in subjects who have in their opinion normalization or near normalization of hemodynamics on the transthoracic echo.

In a small cohort of subjects treated with oral imatinib for PAH, a responder analysis showed that the treatment duration for a complete hemodynamic response was approximately 3 years ([Speich, 2015](#)). Therefore, the LTE study will continue until 31 December 2025 or until the Sponsor stops the study.

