5.5 Down Titration

If a subject down titrated the dose of AV-101 in Study AV-101-002 and successfully completed 24 weeks of treatment, the subject should begin the LTE study with 2 capsules BID at the assigned dose i.e., either re-randomized if coming from placebo or continuing on the randomized dose but at two capsules BID if on active. If the subject does not tolerate the 2 capsules, they may down titrate to one capsule in the LTE. At the time of optimal dose selection and the transition to the optimal dose in subjects who have down titrated in the LTE, the investigator should decide whether it is clinically appropriate to transition these subjects to the optimal dose given the tolerability history and optimal dose selection (Investigators will be unblinded to treatment dose at this time). E.g., if a subject in the 10 mg dose group has to down titrate to one capsule (5 mg) then it is likely inappropriate to transition the subject to 70 mg if that is the chosen optimal dose for Phase 3 and LTE; however, this decision should be based on the Investigator's opinion. Down titration to one capsule BID after being switched to the optimal dose in the LTE will be permitted.

If a subject develops intolerable adverse events during the study, a down titration from two capsules to one capsule will be allowed. The Investigator should conduct an Unscheduled telephone or video visit with the subject to discuss and decide whether down titration to a lower dose is warranted. Careful consideration should be made whether to down titrate or not, and the decision to down titrate should be made when the alternative would be to withdraw study treatment due to drug intolerability. The Investigator should capture any adverse or clinical worsening events, and in cases where the Investigator agrees that down titration is appropriate, the CRO Medical Monitor should be notified as soon as possible. Subjects will not be allowed to up-titrate after having down titrated.

If it is determined by the Investigator that down titration is warranted, the subject will be instructed to take only 1 capsule BID from the assigned study drug bottles. The date and reason for down titration must be recorded in the subject's source documents and in the eCRF.

Down titration is also required if an ECG reveals, for a subject, a QTc interval that exceeds 500 msec, or a QTc progression of ≥ 60 msec (see [Section 5.9.2](#)).

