5.9.2 Prohibited Medicines

The following treatments are not permitted during the study:

- Inhaled prostacyclin therapies
- Warfarin (or any vitamin K antagonists), DOACs or dual antiplatelet therapy

Use of any of the above nonpermitted medicines and therapies require IMP discontinuation (see [Section 6.8](#)) (anti-platelet monotherapy with e.g. aspirin or clopidogrel is allowed).

The use of strong CYP3A4 inhibitors may increase the systemic exposure to imatinib. Likewise, strong CYP3A4 inducers may decrease the exposure of imatinib. It is unknown what contribution of systemically circulating AV-101 will contribute to potential efficacy or adverse events and so alternatives to strong CYP3A4 inhibitors or inducers should be considered.

High doses of oral imatinib are known to have the potential to prolong the QTc interval on the ECG. Drugs that are known to increase the QT interval should be used with caution. For a list of such drugs please refer to <https://crediblemeds.org>. In the event that a subject develops an absolute prolongation of the QTc interval to a value > 500 msec, or develops a change from baseline in the QTc interval of ≥ 60 msec, the subject should undergo a dose reduction. If a subject has already undergone a dose reduction for other reasons, then they should discontinue study drug. The subject should return for an unscheduled visit after two weeks of dose reduction and the ECG should be repeated. If there is a shortening of the QTc interval to < 500 msec, or the change from baseline is

now < 60 msec, the subject should remain on the reduced dose. If there is no change in the QTc interval after reducing the dose then the subject should be discontinued from study drug.

6 Study Assessments and Procedures

Before subjects commence any study-specific activities or procedures, including Week 24 assessments from AV-101-002 which will serve as baseline for this study, the Sponsor requires a copy of the study site's written Independent Ethics Committee/Institutional Review Board (IEC/IRB) approval of the protocol, informed consent form (ICF), and all other subject information and/or recruitment material, if applicable. Each subject must sign and date the ICF before participating in study-specific activities. If an unexpected circumstance occurs that would prohibit the subject from entering the study at Week 24 on AV-101-002, this may be discussed with the CRO Medical Monitor and/or Sponsor.

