6.5.3 Resting Electrocardiogram (ECG)

Digital 12-lead ECGs for all subjects will be recorded at the site using an appropriate ECG machine.

- A standard, single, digital 12-lead ECG will be obtained as outlined in the Schedule of Assessments after the subject has been resting in the supine position for 5 minutes using an ECG machine that automatically calculates the heart rate and measures PR, RR, QRS, QT, and QTc intervals.

All digital ECGs will be documented by recording date and time of collection. All ECG results must be reviewed at the site by the Investigator or a medically qualified designee for clinical management of the subject. The Investigator will judge the overall interpretation as normal or abnormal. Clinical significance and the reason for the abnormality will be recorded in the source documents and in the eCRF. Abnormal values will not be recorded as AEs unless they are a clinically significant change and/or the reason for discontinuation of the study drug due to AEs or are SAEs.

If an ECG result reveals a QTc interval that exceeds 500 msec, or a QTc progression of ≥ 60 msec from baseline, the subject must follow the instructions for down titration of investigational product per [Section 5.5](#) (Also see [Section 5.9.2](#)).

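### A dose reduction made for QTc can be reversed by investigator discretion at the optimal-dose transition, and no ECG is tied to that dose increase.

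*Combined protocol and SAP*

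**What the plan says.** **QTc and dose.** Section 5.5: "Down titration is also required if an ECG reveals, for a subject, a QTc interval that exceeds 500 msec", or if it has lengthened by at least 60 msec. Section 6.5.3 gives the same trigger ("If an ECG result reveals a QTc interval that exceeds 500 msec") and refers back to 5.5. Section 5.9.2 calls for a repeat ECG after two weeks on the lower dose. If QTc has come back under either limit, "the subject should remain on the reduced dose"; if it has not changed, study drug stops.

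**The transition.** For subjects down titrated in the LTE, Section 5.5 says "the investigator should decide whether it is clinically appropriate to transition these subjects to the optimal dose", and the synopsis (Test Product, Dose, and Mode of Administration) says "the Investigator should decide whether it is clinically appropriate to transition these subjects given the tolerability history and optimal dose selection". Neither separates a QTc reduction from one made for tolerability. Section 5.5 calls a move from 5 mg to 70 mg likely inappropriate, but leaves even that to the investigator's opinion.

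**Other texts on the same step.** Section 5.5, second paragraph: "Subjects will not be allowed to up-titrate after having down titrated". Table 1, note 1: "All LTE participants will be treated with the optimal dose once that dose is identified, unless participants have been down titrated". Section 3.1: "Once the optimal dose has been selected subjects in the LTE will be transitioned to the optimal dose", with no exception; Section 1.4 and Figure 1 note B say the same.

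**ECGs.** Table 1 schedules a 12-lead ECG at Screening/Baseline, Week 4, Week 24 and Early Discontinuation or End of Treatment (ED/EOT). The row is blank at Week 12 and at the 12-weekly visits after Week 24, although drug is dispensed at all of those.

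**The concern.** A QTc reduction is mandatory and set by a threshold. The transition clause lets it be undone on a judgement about how well the drug was tolerated. QTc prolongation can be silent, so a patient may look fully tolerant and still be one whom Section 5.9.2 meant to keep at the lower dose.

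The QTc rule also acts only on an ECG result. If the dose goes up when no ECG is due, the rule has nothing to work on, and prolongation would come to light only through an unscheduled ECG or after symptoms. This second gap also covers subjects who were never reduced but whose dose steps up at the transition.

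**Working it through.** The plan gives no figure on this point, so there is none to reproduce. The check compares the rules, then works out when the transition is an increase and how far off the next ECG is.

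**Inputs**
- Reduced doses, one capsule BID: 5, 17.5, 35 mg (synopsis; Sections 5.1 and 5.5).
- Possible optimal doses, two capsules BID: 10, 35, 70 mg (synopsis; Section 1.4).
- Scheduled ECG days: 1, 29, 169, then ED/EOT (Table 1).
- Clinic and dispensing days: 1, 29, 85, 169, then every 12 weeks, i.e. 84 days (Table 1).

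**Step 1. The rules for a subject at one capsule after a QTc reduction**

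| Text | Result at the transition |
|---|---|
| 5.9.2 | Stay on the reduced dose |
| 5.5, first paragraph; synopsis | Investigator decides |
| 5.5, second paragraph | No up-titration |
| Table 1 note 1 | Excepted from the move |
| 3.1, 1.4, Figure 1 note B | Move, no exception stated |

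No text ranks these.

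**Step 2. Dose ratio = optimal dose ÷ reduced dose**

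| Reduced (mg BID) | Optimal 10 | Optimal 35 | Optimal 70 |
|---|---|---|---|
| 5 | 10/5 = 2 | 35/5 = 7 | 70/5 = 14 |
| 17.5 | 10/17.5 = 0.57 | 35/17.5 = 2 | 70/17.5 = 4 |
| 35 | 10/35 = 0.29 | 35/35 = 1 | 70/35 = 2 |

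Six of nine are increases, one is equal and two are decreases. Three of the six (the 2-fold ones) are a return to two capsules of the same strength; the other three (4-, 7- and 14-fold) move to a higher strength.

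For subjects never reduced, the possible increases are 70/35 = 2, 35/10 = 3.5 and 70/10 = 7.

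**Step 3. Days to the next scheduled ECG = next ECG day − day of the rise**

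This assumes the rise falls on a clinic day, which the protocol does not require.

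| Rise at | Next scheduled ECG |
|---|---|
| Week 4 (Day 29) | 169 − 29 = 140 days |
| Week 12 (Day 85) | 169 − 85 = 84 days |
| Week 24 (Day 169) or later | None until ED/EOT |

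For a rise between visits after Day 29 and before Day 169, the gap is 169 minus the day of the rise. After Day 169 the result does not depend on the assumption. The only ECG tied to any dose change is the repeat two weeks after a reduction (5.9.2).

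**The case against.** The texts can largely be read together. Section 3.1 is an overview. Table 1 note 1 takes down-titrated subjects out of the automatic move. The first paragraph of 5.5 then says what happens to them: the investigator decides. The up-titration ban sits in the paragraph on going from two capsules to one, and may bar only a return to two capsules of that strength. The 5.9.2 sentence states the outcome of a two-week repeat ECG and does not mention the transition. The investigator is unblinded to dose by then, reviews every ECG (6.5.3), has the recorded reason for the reduction (5.5), and may order an unscheduled ECG. Section 5.9.2 ties the QTc concern to high doses of oral imatinib, and Section 1.2.1 reports lower systemic exposure with AV-101 and no clinically important ECG changes at up to 90 mg BID.

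Much of this stands. A reader might infer that three texts squarely forbid what a fourth allows. The documents do not support that, because note 1 and the ban can sit beside the discretion clause. They still add to the ambiguity: if the ban covers only a return to two capsules of the same strength, it bars the 2-fold steps and leaves the 4-, 7- and 14-fold steps open, which can hardly be intended.

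Section 5.9.2 is not reconciled. It is the specific rule for QTc, it sets no end date, and the discretion clause does not exclude the subjects it covers. The Phase 1 data come from healthy volunteers dosed for 7 days, and the protocol still thought the risk worth a mandatory reduction. The option of an unscheduled ECG does not close the gap, since nothing prompts one when the dose rises.

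**Conclusion.** The point holds as a gap between 5.9.2 and the discretion in 5.5 and the synopsis, together with the lack of any ECG tied to a dose rise at the transition. It should be fixed before the transition takes place.

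Its size is bounded but not known. The documents do not give the number of QTc reductions or the date of dose selection, and the number affected may be small. The rule conflict matters only where the optimal dose exceeds the reduced dose.

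Four stronger inferences are not supported:
- **That six of nine is a risk.** It counts combinations and is not a probability; 5.5 itself discourages the 14-fold one.
- **That AV-101 prolongs QTc at these doses.** The documents give no such evidence.
- **That dose rises at LTE entry go unmonitored.** The Baseline and Week 4 ECGs cover them. The gap concerns subjects already in the LTE when the dose is selected.
- **That subjects reduced for QTc in AV-101-002 are wrongly restarted on two capsules.** The parent study's QTc rules are not in the file, so this cannot be judged.

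**What to change.** **1. Settle precedence.** In Section 5.5 and the synopsis, state: *A subject whose dose was reduced for QTc (Section 5.9.2) must not move to a BID dose above the reduced dose at the optimal-dose transition. If the optimal dose is equal or lower, or the reduction was for another reason, the Investigator decides.* Add that this decision is the only exception to the no-up-titration sentence. Cross-refer to it from Table 1 note 1, Sections 1.4 and 3.1, and Figure 1 note B. Keep the lower strengths in supply for subjects held: 5 mg capsules if the optimal dose is 35 or 70 mg, and also 17.5 mg capsules if it is 70 mg. In the other three increases, the optimal-dose capsule already serves.

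**2. Tie ECGs to the rise.** In Table 1, for any subject whose BID dose rises at the transition, make the change at a scheduled clinic visit, with a 12-lead ECG before the higher dose. Repeat it no later than the next scheduled clinic visit, and preferably at about two weeks, matching the repeat ECG in 5.9.2. The outer limit alone leaves 85 − 29 = 56 days after a Week 4 rise and 84 days after a Week 12 or later rise. For a Week 12 rise it adds only the pre-dose ECG, because Week 24 already has one. That is why two weeks is better.

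**Cost.** A few sentences, and one or two extra ECGs per affected subject. The two-week repeat may need a short unscheduled visit. The transition may wait up to 12 weeks for a clinic visit. Lower strengths stay in supply in three combinations, which the existing discretion already implies.

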5.6 Randomization, Blinding, and Measures to Minimize Bias

An interactive web-based randomization system (IWRS) will be used to randomize a previously placebo-treated subject to study drug assignment in the period prior to identification of the optimal dose. Subjects randomized to active treatments in the parent study will remain in their previously assigned active treatment until the optimal dose is identified.

Once a previously placebo treated subject meets the eligibility criteria and is enrolled, the subject will be randomly assigned to a unique randomization number that is associated with the treatment assignment per the randomization list. The subject identification in the parent and LTE trials will remain the same. In addition, the IWRS will allocate study drug to subjects according to the Schedule of Assessments ([Table 1](#)).

Before the study is initiated, the log-in information and directions for the IWRS will be provided to each site.

5.7 Study Drug Preparation, Handling, Storage, and Accountability

Acquisition

The investigational product will be supplied to the clinical site directly from a depot or warehouse as required.

Storage

The kits should be stored in a dry place between 20°C to 25°C (68°F to 77°F), excursions permitted to 15°C to 30°C (59°F to 86°F).

Handling

Packaged clinical kits must be handled and stored as units.

Accountability

The Investigator, institution, or the head of the medical institution (where applicable) is responsible for study drug accountability, reconciliation, and record maintenance (i.e., receipt, reconciliation, and final disposition records).

- Upon receipt of the study drug, the Investigator or designee must confirm appropriate temperature conditions have been maintained during transit and any discrepancies are reported and resolved before use. Only subjects enrolled in the study may receive study drug and only authorized site staff may supply it.
- Study drug accountability records at the study site will include the following:
 - Confirmation of receipt, in good condition and in the defined temperature range
 - The dose each subject used during the study
 - The disposition (including return, if applicable) of any unused study drug
 - Dates, quantities, study drug number, expiry dates, and the subject numbers
- The Investigator site will maintain records, which adequately document that subjects were provided the dose specified in this protocol, all study drug provided was fully reconciled, and all study drug and device complaints have been documented.
- Unused study drug must not be discarded or used for any purpose other than the present study prior to accountability being performed by the Study Monitor. No study drug or inhaler that is dispensed to a subject may be re-dispensed to a different subject.
- Used and unused devices should be returned by the subject to the site unless otherwise indicated per local policy.

- A Study Monitor will periodically collect the study drug accountability forms.
- Further guidance and information for the final disposition of unused study drug, and study relevant forms such as those to report study drug and device deficiencies, complaints, and incidents are provided in the Pharmacy Manual.

Device and Study Drug Disposal (if applicable):

Devices will be disposed of according to the Pharmacy Manual.

Destruction of used and unused study drug should be performed at the site if allowed by local law only after Sponsor/designee authorization. If that is not possible, the Sponsor/designee will be responsible.

